7.2.3 Resource utilization

Not applicable.

7.2.4 Patient reported outcomes

Not applicable.

8 Safety monitoring and reporting

8.1 Adverse events

8.1.1 Definitions and reporting

An adverse event is defined as the appearance of (or worsening of any pre-existing) undesirable sign(s), symptom(s), or medical condition(s) that occur after patient's signed informed consent has been obtained.

Abnormal laboratory values or test results occurring after informed consent constitute adverse events only if they induce clinical signs or symptoms, are considered clinically significant, require therapy (e.g., hematologic abnormality that requires transfusion or hematological stem cell support), or require changes in study medication(s).

Adverse events that begin or worsen after informed consent should be recorded in the Adverse Events CRF. Conditions that were already present at the time of informed consent should be recorded in the Relevant Medical History page of the patient's CRF. Adverse event monitoring should be continued for at least 30 days following the last dose of study treatment. Adverse events (including lab abnormalities that constitute AEs) should be described using a diagnosis whenever possible, rather than individual underlying signs and symptoms. When a clear diagnosis cannot be identified, each sign or symptom should be reported as a separate Adverse Event.

Adverse events will be assessed and graded according to the Common Terminology Criteria for Adverse Events (CTCAE) version 4.03. Grade 1 to 5 will be used to characterize the severity of the Adverse Event.

If CTCAE grading does not exist for an adverse event, the severity of mild, moderate, severe, and life-threatening, death related to the AE corresponding respectively to Grades 1 - 5, will be used. Information about any deaths (related to an Adverse Event or not) will also be collected through a Death form.

The occurrence of adverse events should be sought by non-directive questioning of the patient (subject) during the screening process after signing informed consent and at each visit during the study. Adverse events also may be detected when they are volunteered by the patient (subject) during the screening process or between visits, or through physical examination, laboratory test, or other assessments. As far as possible, each adverse event should be evaluated to determine:

1. The severity grade (CTCAE Grade 1-5)
2. Its duration (start and end dates or ongoing at end of study)
3. Its relationship to the study treatment (reasonable possibility that AE is related: No, Yes)
4. Action taken with respect to study or investigational treatment (none, dose adjusted, temporarily interrupted, permanently discontinued, unknown, not applicable)
5. Whether medication or therapy was given (no concomitant medication/non-drug therapy, concomitant medication/non-drug therapy)
6. Whether it is serious, where a serious adverse event (SAE) is defined as in [Section 8.2.1](#) and which seriousness criteria have been met

7. Outcome (not recovered/not resolved, recovered/resolved, recovered/resolved with sequelae, fatal, unknown)

If the event worsens the event should be reported a second time in the CRF noting the start date when the event worsens in toxicity. For grade 3 and 4 adverse events only, if improvement to a lower grade is determined a new entry for this event should be reported in the CRF noting the start date when the event improved from having been Grade 3 or Grade 4.

All adverse events should be treated appropriately. If a concomitant medication or non-drug therapy is given, this action should be recorded on the concomitant medication CRF.

Once an adverse event is detected, it should be followed until its resolution or until it is judged to be permanent, and assessment should be made at each visit (or more frequently, if necessary) of any changes in severity, the suspected relationship to the study treatment, the interventions required to treat it, and the outcome.

8.1.2 Laboratory test abnormalities

8.1.2.1 Definitions and reporting

Laboratory abnormalities that constitute an Adverse event in their own right (are considered clinically significant, induce clinical signs or symptoms, require concomitant therapy or require changes in study treatment), should be recorded on the Adverse Events CRF. Whenever possible, a diagnosis, rather than a symptom should be provided (e.g. anemia instead of low hemoglobin). Laboratory abnormalities that meet the criteria for Adverse Events should be followed until they have returned to normal or an adequate explanation of the abnormality is found. When an abnormal laboratory or test result corresponds to a sign/symptom of an already reported adverse event, it is not necessary to separately record the lab/test result as an additional event.

Laboratory abnormalities, that do not meet the definition of an adverse event, should not be reported as adverse events. A Grade 3 or 4 event (severe) as per CTCAE does not automatically indicate a SAE unless it meets the definition of serious as defined below and/or as per investigator's discretion. A dose hold or medication for the lab abnormality may be required by the protocol in which case the lab abnormality would still, by definition, be an adverse event and must be reported as such.

8.1.3 Adverse events of special interest

Adverse events of special interest (AESI) are defined as events (serious or non-serious) which are ones of scientific and medical concern specific to the sponsor's product or program, for which ongoing monitoring and rapid communication by the investigator to the sponsor may be appropriate. Such events may require further investigation in order to characterize and understand them.

Adverse events of special interest are defined on the basis of an ongoing review of the safety data.

8.2 Serious adverse events

8.2.1 Definitions

Serious adverse event (SAE) is defined as one of the following:

- Is fatal or life-threatening
- Results in persistent or significant disability/incapacity
- Constitutes a congenital anomaly/birth defect
- Is medically significant, i.e., defined as an event that jeopardizes the patient or may require medical or surgical intervention to prevent one of the outcomes listed above
- Requires inpatient hospitalization or prolongation of existing hospitalization,
- Note that hospitalizations for the following reasons should not be reported as serious adverse events:
 - Routine treatment or monitoring of the studied indication, not associated with any deterioration in condition
 - Elective or pre-planned treatment for a pre-existing condition that is unrelated to the indication under study and has not worsened since signing the informed consent
 - Social reasons and respite care in the absence of any deterioration in the patient's general condition
- Note that treatment on an emergency outpatient basis that does not result in hospital admission and involves an event not fulfilling any of the definitions of a SAE given above is not a serious adverse event

8.2.2 Reporting

To ensure patient safety, every SAE, regardless of suspected causality, occurring after the patient has provided informed consent and until at least 30 days after the patient has stopped study treatment must be reported to Novartis within 24 hours of learning of its occurrence.

Any additional information for the SAE including complications, progression of the initial SAE, and recurrent episodes must be reported as follow-up to the original episode within 24 hours of the investigator receiving the follow-up information. An SAE occurring at a different time interval or otherwise considered completely unrelated to a previously reported one should be reported separately as a new event.

Any SAEs experienced after the 30 day safety evaluation follow-up period should only be reported to Novartis if the investigator suspects a causal relationship to the study treatment.

Information about all SAEs is collected and recorded on the Serious Adverse Event Report Form; all applicable sections of the form must be completed in order to provide a clinically thorough report. The investigator must assess and record the relationship of each SAE to study treatment, complete the SAE Report Form in English, and submit the completed form within 24 hours to Novartis. Detailed instructions regarding the SAE submission process and requirements for signatures are to be found in the investigator folder provided to each site

Each re-occurrence, complication, or progression of the original event should be reported as a follow-up to that event regardless of when it occurs. The follow-up information should

describe whether the event has resolved or continues, if and how it was treated, whether the blind was broken or not, and whether the patient continued or withdrew from study participation.

If the SAE is not previously documented in the Package Insert (new occurrence) and is thought to be related to the Novartis study treatment, an oncology Novartis Chief Medical Office and Patient Safety (CMO&PS) department associate may urgently require further information from the investigator for Health Authority reporting. Novartis may need to issue an Investigator Notification (IN), to inform all investigators involved in any study with the same drug that this SAE has been reported. Suspected Unexpected Serious Adverse Reactions (SUSARs) will be collected and reported to the competent authorities and relevant ethics committees in accordance with Directive 2001/20/EC or as per national regulatory requirements in participating countries.

8.3 Pregnancies

To ensure patient safety, each pregnancy occurring while the patient is on study treatment must be reported to Novartis within 24 hours of learning of its occurrence. The pregnancy should be followed up to determine outcome, including spontaneous or voluntary termination, details of the birth, and the presence or absence of any birth defects, congenital abnormalities, or maternal and/or newborn complications.

Pregnancy should be recorded on a Clinical Trial Pregnancy Form and reported by the investigator to the oncology Novartis Chief Medical Office and Patient Safety (CMO&PS). Pregnancy follow-up should be recorded on the same form and should include an assessment of the possible relationship to the study treatment any pregnancy outcome. Any SAE experienced during pregnancy must be reported on the SAE Report Form.

Pregnancy outcomes should be collected for the female partners of any males who took study treatment in this study. Consent to report information regarding these pregnancy outcomes should be obtained from the mother.

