5.2 Inclusion criteria

Patients eligible for inclusion in this study have to meet **all** of the following criteria:

1. Eligible for treatment with everolimus as per the locally approved label.
2. Presence of at least one AML ≥ 3 cm in its longest diameter using CT or MRI.
3. If female of child bearing potential, documentation of negative pregnancy test at time of Screening. Females of child-bearing potential, defined as all women physiologically capable of becoming pregnant, must use highly effective methods of contraception during dosing and for 8 weeks after stopping medication. Highly effective contraception methods include:
 - Total abstinence: When this is in line with the preferred and usual lifestyle of the subject. [Periodic abstinence (e.g., calendar, ovulation, symptothermal, post-ovulation methods) and withdrawal are not acceptable methods of contraception]
 - Female sterilization: have had surgical bilateral oophorectomy (with or without hysterectomy) or tubal ligation at least six weeks before taking study treatment. In case of oophorectomy alone, only when the reproductive status of the woman has been confirmed by follow up hormone level assessment
 - Male partner sterilization (at least 6 months prior to screening). The vasectomized male partner should be the sole partner for that subject.
 - Use of oral, injected or implanted hormonal methods of contraception or placement of an intrauterine device (IUD) or intrauterine system (IUS), or other forms of hormonal contraception that have comparable efficacy (failure rate $<1\%$), for example hormone vaginal ring or transdermal hormone contraception.

In case of use of oral contraception women should have been stable on the same pill for a minimum of 3 months before taking study treatment

4. Sexually active males must use a condom during intercourse while taking the drug during treatment, and for 8 weeks after stopping treatment. They should not father a child in this period. A condom is required to be used also by vasectomized men as well as during intercourse with a male partner in order to prevent delivery of the drug via semen.
5. Written informed consent according to local guidelines must be obtained prior to any screening procedures.

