7.1 Study flow and visit schedule

Table 7-1 lists all of the assessments and indicates with an “X” the visits when they are performed. All data obtained from these assessments must be supported in the patient’s source documentation.

The table indicates which assessments produce data to be entered into the clinical database (D) or remain in source documents only (S) (“Category” column). No CRF will be used as a source document.

Allowed visit windows are specified as follows:

- Screening assessments as listed in Table 7-1 should occur within 28 days prior to Day 1.
- The 4, 12, 24, and 48 weeks visits should be performed within a ± 7 day window.

[figure not shown]
- The 12, 24, and 48 weeks efficacy follow-up visits, where applicable, should be performed within a ± 7 day window.
- Urine pregnancy tests (when applicable) should be performed every 4 weeks during the treatment phase within a ± 7 day window.
- The End of Treatment (EOT) visit should be performed within 28 days of last dose.
- All patients should be followed for at least 30 days for AEs and SAEs after last dose.

Every effort should be made to follow the schedule outlined in [Table 7-1](#).

[figure not shown]

Table 7-1 Visit evaluation schedule

[figure not shown]
Visit Name	Category	Protocol Section	Screening	Open Label Treatment								Treatment Discontinuation Follow-up
				Day 1	Week 4	Week 12	Week 24	Week 48	Every 4 weeks after Week 4 until EOT	End of study treatment (EOT)	Safety follow-up (Last dose +30days)	
Visit number			1	100	110	120	130	140		1999		1010,1020,1030
Visit window			-28 to -1 days		±7days	±7days	±7days	±7days	±7days	Within 28 days from last dose	+7 days	±7days
Obtain Informed Consent	D	11.3	X									
Demography	D	7.1.2.3	X									
Inclusion/exclusion criteria	D	5.2 5.3	X	X								
TSC diagnosis	D	7.1.2	X									
Relevant medical history	D	7.1.2.3	X									
HIV history	S	7.1.2.3	X									
Prior/concomitant medications	D	7.1.2.3	X	X	X	X	X	X		X	X	
Physical examination	S	7.2.2.1	X	X	X	X	X	X		X		
WHO Performance status	D	7.2.2.4	X	X	X	X	X	X		X		
Height	D	7.2.2.3	X									
Weight	D	7.2.2.3	X	X	X	X	X	X		X		

[figure not shown]
Visit Name	Category	Protocol Section	Screening	Open Label Treatment								Treatment Discontinuation Follow-up	
				Day 1	Week 4	Week 12	Week 24	Week 48	Every 4 weeks after Week 4 until EOT	End of study treatment (EOT)	Safety follow-up (Last dose +30days)		
Visit number			1	100	110	120	130	140		1999		1010,1020,1030	

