7.2.2.5.5 Pregnancy

Female patients of child bearing potential will perform urine pregnancy tests as outlined in [Table 7-1](#) every 4 weeks (± 7 days) while receiving study drug until study drug discontinuation. The urine tests will be performed at the patient's home or at clinical site when a visit is scheduled. Patients should be instructed to inform site of a positive urine pregnancy result. A serum hCG pregnancy test should be performed by the central lab at screening and at end of treatment.

The results of urine pregnancy tests will be recorded in the patient source documents (pregnancy diary, patient records) whereas serum pregnancy test results will be recorded in the database of the assigned central lab vendor.

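### Pregnancy reporting for female patients covers only time on study treatment, although the protocol's own contraception window runs 8 weeks past the last dose

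*Protocol*

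**What the plan says.** **The reporting duty.** Protocol Section 8.3 states that "each pregnancy occurring while the patient is on study treatment must be reported to Novartis", with a 24-hour limit that starts when the site learns of it. The pregnancy is then to be followed to its outcome, including any birth defect and maternal or newborn complications. For male patients the same section says: "Pregnancy outcomes should be collected for the female partners of any males who took study treatment in this study". That sentence has no end date, and it states no 24-hour deadline.

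**The precaution window.** Under inclusion criterion 3 in Section 5.2, women of child-bearing potential "must use highly effective methods of contraception during dosing and for 8 weeks after stopping medication". Criterion 4 sets the same length for men, with condom use "for 8 weeks after stopping treatment. They should not father a child in this period".

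**Testing and contact after the last dose.** Section 7.2.2.5.5 schedules urine tests every 4 weeks "while receiving study drug until study drug discontinuation", and adds: "A serum hCG pregnancy test should be performed by the central lab at screening and at end of treatment". On the timing of that last test, Section 7.1 says: "The End of Treatment (EOT) visit should be performed within 28 days of last dose". Section 7.1.6 requires safety evaluation for 30 days after the last dose, by visit or telephone, and names the adverse event and concomitant medication forms. Table 7-1 gives the safety follow-up visit a +7 day window.

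**Other safety reporting.** Section 8.1.1 continues adverse event monitoring for at least 30 days after the last dose. Section 8.2.2 requires all SAEs to be reported to at least 30 days, and later ones only when the investigator suspects causality.

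**The concern.** The protocol uses one time span to prevent pregnancy and a shorter one to learn about it. It asks women to avoid conception for 8 weeks after stopping, yet its duty to report and follow a pregnancy in a patient is tied to being on study treatment. That is also shorter than the tail given to adverse events and SAEs.

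The protocol can therefore produce information that it does not require anyone to act on. A positive serum test at the End of Treatment visit may reflect conception after the last dose. A patient may mention a new pregnancy at the safety contact. Section 8.3 obliges the site neither to report it nor to follow it to outcome. An uncomplicated pregnancy is not an SAE under Section 8.2.1, so the SAE route does not trigger follow-up either.

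What is at stake is complete safety follow-up in a post-approval study of about 40 patients whose primary objective is safety. At that size a single pregnancy with unknown outcome would be a visible omission.

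**Working it through.** The plan gives no figure for this point to reproduce. The check sets the windows side by side and counts days.

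**Inputs**
- Contraception window after last dose: 8 weeks (Section 5.2, criteria 3 and 4).
- Mandatory pregnancy reporting after last dose, female patients: 0 days (Section 8.3).
- Last scheduled pregnancy test: End of Treatment, at most 28 days after last dose (Sections 7.1 and 7.2.2.5.5).
- Safety contact: day 30, with +7 days allowed (Section 7.1.6, Table 7-1).
- Mean elimination half-life: about 30 hours (Section 1.2.3).

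**Arithmetic**

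| Quantity | Calculation | Result |
|---|---|---|
| Precaution window | 8 × 7 | 56 days |
| Window outside the reporting duty | 56 − 0 | 56 days |
| Window left after the latest End of Treatment test | 56 − 28 | 28 days (more if the test is earlier) |
| Window left after safety contact on day 30 | 56 − 30 | 26 days |
| Window left after safety contact on day 37 | 56 − 37 | 19 days |
| Five half-lives | 5 × 30 ÷ 24 | 6.25 days |
| Window in half-lives | 56 × 24 ÷ 30 | 44.8 |

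**Which pregnancies are affected**
1. *Female patient, begun on treatment, found later.* Reportable: the 24 hours run from when the site learns of it.
2. *Female patient, conceived after the last dose, within 56 days.* Outside Section 8.3, whether found at End of Treatment, at the safety contact or later. No other section brings it in.
3. *Female partner of a male patient.* Outcome collection applies without a time limit.
4. *SAE during a pregnancy of type 2.* Reportable to at least 30 days, and afterwards only if causality is suspected. A congenital anomaly would normally become known after day 30 and so would depend on that suspicion.

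The gap is therefore type 2, apart from the SAEs that the route in type 4 picks up. The documents do not give the number of women of child-bearing potential, so no expected count can be calculated.

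**The case against.** Several counter-arguments have force.

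**Margin by design.** A contraception window can be wider than a reporting window on purpose. With a half-life of about 30 hours, five half-lives pass in 6.25 days and the full window is about 45 half-lives. Late in the 8 weeks, residual drug would be very small. This stands against calling these pregnancies exposed, a word the protocol does not use for the window. It does not explain why the reporting tail for pregnancy is shorter than the 30 days given to every adverse event.

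**The meaning of on treatment.** Section 10.4.1 defines the on-treatment period as running to 30 days after the last dose. Section 8.3 does not refer to it, and it is an analysis definition. Even if it were read into Section 8.3, 56 − 30 = 26 days would stay uncovered.

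**Harm is caught elsewhere.** Congenital anomaly is an SAE criterion, and Section 8.3 sends any SAE during pregnancy to the SAE form. This partly stands, but without a pregnancy report nothing prompts anyone to look for the outcome.

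**A stronger reading.** A reader might infer that all pregnancy reporting stops with treatment, or that the primary analysis is compromised. The documents support neither. Partner outcomes are open-ended, and pregnancies begun on treatment remain reportable whenever found. The planned safety tables count adverse events and laboratory abnormalities to 30 days after the last dose, so an uncomplicated later pregnancy changes none of them.

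**Timing.** At Amendment 2 all 40 patients were enrolled and on treatment, and patients may move to commercial drug at study end (Section 4.2). For those patients, the 8 weeks after study dosing are not drug-free.

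**Conclusion.** The inconsistency between Sections 5.2 and 8.3 is real and limited. It concerns pregnancies in female patients conceived after the last study dose and within the protocol's own 56-day window. For these, reporting and outcome follow-up are not required at any point in the window. From 19 to 26 days of it also fall after the last scheduled safety contact.

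The conclusion rests on two readings: that Section 8.3 means what it says by on study treatment, and that the contraception window is the sponsor's own statement of how long precaution is warranted. It does not rest on any claim about drug levels late in that window.

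The consequence is incomplete safety follow-up for a rare event. Sample size, the efficacy analysis and the planned primary tables are unaffected. This is a minor point that is cheap to put right.

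**What to change.** Reconcile Section 8.3 with Section 5.2:
- State that the reporting and outcome follow-up duty for female patients runs from first dose to the end of the post-treatment contraception window that the protocol already sets.
- Keep the provision on female partners of male patients open-ended. Putting an 8-week limit on it would narrow the present duty.
- At the existing 30-day safety contact, ask about pregnancy and remind patients to report one that arises in the rest of the window. The question alone cannot detect conceptions after the contact, so the reminder is needed as well.

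This uses the existing pregnancy form and contact and adds no test. The cost is a written amendment with the approvals in Section 12.1, plus possible late reports after the last visit. Days after the safety contact would still depend on patients coming forward.

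SAP Section 2.7.1 describes observations made at database lock, so for this trial the practical step may be a single query to sites about pregnancies in the window. The corrected wording would then serve later protocols.
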